As Vapotherm Hi-VNI technology becomes more common-place in hospital standard of care & practice, HVNI therapy may also have a demonstrable effect on improving patient ambulation and mobility. Mobility represents a key factor in the timely improvement of patient health, and in end-of-life cases it can have a mental impact⁸. In addition to the patient benefits, ambulation and early ambulation & mobility can also reduce the patient hospital resource allocation and reduce the length of stay (LOS). Some hospitals have included patient ambulation metrics as a key success factor, and this also can play a role to stepping-down

Vapotherm, Inc

HVNI Ambulation Feasibility Study

Confidential

the patients to less critical care environments. The goal of this study is to establish a low risk model, modified from the 6MWT, for patients with dyspnea: (1) evaluate the effect of HVNI on ambulation, and (2) assess the impact HVNI use may have on improved outcomes when compared to standard TAU (HVNI).

Vapotherm, Inc
HVNI Ambulation Feasibility Study
Confidential

II. Overall Study Objective

The **overall objective** of this study is to evaluate the ability of HVNI to improve patient ambulation relative to a treatment as usual (TAU).

The **hypothesis** is that HVNI therapy, when implemented in conjunction to ambulatory practices, will be more effective than TAU to improve patient mobility by reducing the patient's perceived dyspnea and exertion via maintaining oxygenation (reduced desaturation) and supporting ventilation (reduced work of breathing [WOB]).

To test this hypothesis, the study will be conducted with the following specific aims:

Aim #1: Primary Outcome. The primary endpoint is exercise performance, defined as the distance and duration of patient ambulation.

Aim #2: Secondary Outcomes. The secondary endpoints evaluate the patient recovery interval, defined as the recovery time (return time to baseline perceived dyspnea). Other endpoints will include: vital signs (heart rate [HR], respiratory rate [RR], blood pressure [BP]), arterial oxygen saturation (SpO₂), rated perceived exertion (RPE), and rated perceived dyspnea (RPD).

Aim #3: Tertiary Outcomes. The tertiary endpoints evaluate the clinician perception scores. For the clinician perceptions this will include: technical/clinical difficulties, patient comfort & tolerance, ease of use, monitoring & support for therapy, and expected/perceived patient outcomes.

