This will be a feasibility study, performed as a prospective, crossover trial to evaluate the potential patient improvement during ambulation while on HVNI relative to TAU. Patients who fit the criteria for inclusion will perform ambulation for each study period: the baseline period (TAU) followed by the test period (HVNI). The clinical management will otherwise remain unchanged based on the site SOC practices. The patient FiO_2 and flow values will be recorded while on any supplemental oxygen. Subjects will wear appropriate gear and, when applicable, have mobile carts to provide supplemental oxygen therapy (e.g. HVNI VTU) during ambulation.

This feasibility study design focuses on three distinct phases: (1) baseline characterization, (2) performance measures of ambulation, and (3) clinician perceived satisfaction scores. The baseline characterization is to provide patient background, history, and initial relevant clinical evaluation from Aim 2. Performance

Vapotherm, Inc

HVNI Ambulation Feasibility Study

Confidential

measures from Aims 1 & 2 will provide physiologic relevant indices before/during/after ambulation session and will be used for meaningful comparison between study arms. Lastly, Aim 3 will provide an overall assessment from the clinician perceived satisfaction scores.

This feasibility study will involve two study periods: baseline (TAU) and test (HVNI). Baseline period will be administered first, followed by the test period. Patients deemed in need of ambulation (per inclusion/exclusion criteria) will be enrolled into the study and will complete both study periods:

1. Treatment as usual (TAU) of standard practices (control arm) for ambulation at site
2. Vapotherm HVNI therapy (test arm) administered as described below during ambulation at site

This feasibility study will be conducted in a research facility and where testing can be performed with appropriate supervision and staff training to maintain patient safety. This current study uses a modified 6MWT ambulation test to evaluate the patient performance. Primary and secondary outcomes will be completed upon the completion of each study arm's ambulation test. Tertiary outcomes will be completed upon study. All respiratory interventions will be tracked during the study window, and disposition and mortality will be tracked for each patient.

V. Subject Enrollment

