Subjects will be solicited by research staff and consented prior to participation in this feasibility study (Aims 1-3). Once consented, the participants will complete all Aims during the course of participation in the study, per the TAU at each site. Compensation will be provided to participants for enrollment into this study.

Sample Size:

To provide a sample data set, we will enroll up to 32 subjects to complete this feasibility assessment, with a calculated sample size of N=26 plus a 20% failure rate. This will provide sufficient initial data to inform the appropriate sample size of a follow-on randomized study.

This sample size was calculated through use of references that approximated similar studies ^{1,32}. McCarthy et al. found a mean difference of 42.93m with 95CI: 32.64 – 55.21m when evaluating patient ambulation with and without adjunctive therapy ³². For this study, using a desired power of 90% with alpha=0.05, the sample size is estimated at 26 to show a difference in data between the control and test groups.

Vapotherm, Inc
HVNI Ambulation Feasibility Study
Confidential

VI. Study Procedures

This feasibility study is non-blinded by necessity, since the provided therapies have different devices. No randomization will be incorporated into this feasibility study design. The study arms will be performed as a crossover design, baseline performed first followed by the test period. Study model for the ambulation test is a modified 6-minute walk test. Figure 1 illustrates an overview of the study procedures. This feasibility study will evaluate the baseline, performance, recovery, and clinical assessment indices to demonstrate the effect between TAU and HVNI during ambulatory practice.

Screening, Enrollment, & Management

Upon screening, subjects will be asked to participate in this study, and if so they will be consented prior to enrollment. Subjects are instructed that if at any time during the study they are free to stop the test and discontinue study participation. All study procedures will be explained to the subject.

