Baseline Characterization will be performed just prior to the next scheduled ambulation test, as deemed appropriate for the patient by the investigator. Sitting down, the subject will be setup and prepared for the ambulation test with appropriate data recording devices and supplementary oxygen (only HVNI). While subject is at rest, standing up, the following data will be collected (see Table 1): RR, HR, BP, SpO₂, and RPD (Modified Borg scale 0-10). For the RPD & RPE, the coordinator will record patient scores. Record the FiO₂ and flow settings for any supplemental oxygen provided to the patient before/during/after this baseline phase.

The Ambulation Test will be performed after the baseline characterization is complete, and in accordance to the standard practice of the site and judgment of the investigator to maintain patient safety. The definition for this ambulation test will be to walk until 18 minutes has elapsed or the patient is unable to continue. A timer will keep track of the test duration, and the clinician will keep track of the distance traveled during ambulation. At test start, test end, & 1-minute intervals the subjects will be asked to rate their RPD & RPE (Modified Borg scale 0-10). The subject vitals will be monitored during this ambulation test and recorded as follows: HR, RR, SpO₂. The ambulation test will end if, the subject has completed 18 minutes, stops walking for more than 10 seconds, has to sit down, has any adverse events, or should the investigator deem necessary.

Recovery Interval will begin immediately following the end of the Ambulation Test. The subject will perform this recovery interval while safely seated. The time to return to the subject's resting-while-standing RPD score (Baseline) will be used as recovery time. At the end of the recovery interval, record the subject RR, HR, BP, SpO₂, and RPD & RPE. Any adverse events will be recorded. Any exacerbations from ambulation walk test will be recorded during the recovery interval. Record the recovery end time and date.

After the Recovery Interval is complete, all associated data will be collected (per Table 1). This includes all end-of-study data prior to study completion including perception/satisfaction scores.

Other Medical Care

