All other pharmaceutical and medical treatment will remain the purview of the attending physician and will be administered per the current standards. This study is designed to evaluate only intervention of HVNI in conjunction with standard (TAU) ambulatory practice, and it is assumed that the ancillary interventions will

Vapotherm, Inc
HVNI Ambulation Feasibility Study
Confidential

follow common clinical practice guidelines and conventions. All treatments given to the subjects will be noted on their CRFs.

VapoTherm, Inc
HVNI Ambulation Feasibility Study
Confidential

VII. Data Collection

Table 1. Key study data and collection points.

	Baseline Characterization	Ambulation Test	Recovery Interval	@ Study End
Patient History & Health	X			X
Treatment: Flow & O2	X	X	X	X
Physiologic Parameters	X	X	X	X
Performance Parameters		X		
Recovery Parameters			X	
Clinician Perception Scores			X	X
Disposition	X			X

Patient enrollment data collection will include patient history, health, demographics, and interventions. For each test session the following data will be recorded for comparison.

Physiologic Parameters

- SpO₂, HR, RR, BP, RPE, RPD

Performance Parameters

- Test duration and test distance traveled

Recovery Parameters

- Return time to baseline RPD, HR, RR, BP, SpO₂, RPD, RPE

Primary Endpoint

- Distance and duration of exercise during ambulation

Secondary Endpoints

- Physiologic parameters – SpO₂, HR, RR, BP, RPE, RPD
- Recovery parameters: return time to baseline Rated Perceived Dyspnea score
- Modified Borg scale scores – Rated Perceived Exertion (RPE), Rated Perceived Dyspnea (RPD)

Tertiary Endpoints

- Clinician perception of patient respiratory response to therapy, ranging from NO Response to Excellent Response, as continuous VAS.
- Clinician perception of frequency of rain-out, interface slippage or other technical/clinical difficulties applying therapy, ranging from Never to Frequent as continuous VAS.
- Clinician perception of patient comfort and tolerance of therapy, ranging from Very Poorly Tolerated to Very Well Tolerated as continuous VAS.

Vapotherm, Inc

HVNI Ambulation Feasibility Study

Confidential

- Clinician perception of Simplicity of set-up and use, ranging from Complex to Setup and Use to Simple to Setup and Use, as continuous VAS.
- Clinician perception of Monitoring and support of therapy required (adjustments, refilling fluids, adjusting interface), ranging from Almost Constantly to Almost Never, as continuous VAS.

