VIII. Statistical Analysis

The data analysis will be “per protocol.” Baseline patient demographics and characteristics will be summarized, and appropriate statistical testing will be performed for the continuous and categorical variables. Assuming a non-normal data distribution for this crossover study design, the non-parametric Wilcoxon Signed Rank Sum test will be performed with significance interval of 0.05 on all applicable variables. Otherwise, for the categorical variables, the Fisher’s Exact test will be performed. Data will be compared and graphed accordingly for a visual comparison with accompanied statistical notations.

IX. Risks and Discomforts

This pilot study does not present significant risk to patients, as supplemental oxygen is routinely provided to patients and the 6MWT is a standard/routine practice³³. The Treatment-as-Usual at the study sites involves the application of simple supplemental oxygen during mobilization. Use of the high flow nasal cannula therapy has no known risks and has been used in the clinical setting for approximately seventeen years without known reports of adverse events related to the administration of high nasal flows when appropriately conditioned to near body temperature and fully humidified. The literature indicates that approximately only 4 cmH₂O of distending pressure may be generated in the upper airway^{34,35} which is well below any known threshold for injury. In addition, it has been demonstrated that delivery of high flows of conditioned gas from a nasal cannula has a positive effect on airway mucosal function^{36,37}. The patients will be closely monitored as part of standard medical practice. Ambulation is implemented as part of the standard care practice for the patients included in this study.

For these reasons, we have determined that this study represents non-significant risk to the subjects, beyond the discomfort related to routine ambulation therapy.

X. Potential Benefits

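### Fisher's exact test is prescribed for categorical variables although every TAU-versus-HVNI comparison is within the same subjects

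*Combined protocol and SAP*

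**What the plan says.** Section VIII gives two test rules. The first reads: "Assuming a non-normal data distribution for this crossover study design, the non-parametric Wilcoxon Signed Rank Sum test will be performed". The second follows directly: "Otherwise, for the categorical variables, the Fisher’s Exact test will be performed". The section does not say which categorical variables are meant, and it does not restrict the second rule to comparisons between different people.

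The design is set out elsewhere in the same document. Section IV describes a study "performed as a prospective, crossover trial to evaluate the potential patient improvement during ambulation while on HVNI relative to TAU", in which patients "will be enrolled into the study and will complete both study periods", TAU first and HVNI second. Section VI adds: "No randomization will be incorporated into this feasibility study design". Section VII says: "For each test session the following data will be recorded for comparison".

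The endpoints in Section VII are distance and duration (primary); vital signs, SpO₂, Borg scores and recovery time (secondary); and continuous visual analogue scores (tertiary). None is categorical in the sense of the Fisher rule.

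**The concern.** Fisher's exact test takes its reference distribution from two independent samples. This trial has one sample measured twice. A test on the 26-versus-26 table of session totals discards the information on which subjects had the event in both sessions, one only, or neither. Its p-value therefore does not answer the within-subject question that the crossover was built to answer. The plan would also treat the same subjects as paired for the Wilcoxon test and as unpaired for categorical data.

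If subjects tend to respond alike in the two sessions, which is plausible for the same patient walking twice but not documented, Fisher's test is over-conservative. A real difference in a common event could then be missed. If the correlation is negative, it rejects more often under the null than exact McNemar does.

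**Working it through.** **Which variables could be affected.** Section VI has adverse events recorded in each session and adds: "Any exacerbations from ambulation walk test will be recorded during the recovery interval". Two further yes/no variables could be derived. One is completion of the 18-minute walk, from the stopping rule in Section VI. The other is desaturation, since the hypothesis in Section II refers to "maintaining oxygenation (reduced desaturation) and supporting ventilation". The plan lists none of these as an endpoint.

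**Inputs.** From the documents: 26 subjects (Section V, calculated sample size) and alpha 0.05 (Sections V and VIII), taken here as two-sided because sidedness is not stated. The plan gives no power for any categorical comparison, so there is no figure of its own to reproduce. Event rates and within-subject correlation (phi) are assumptions.

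**Formulas.** Let p1 and p2 be the event probabilities on TAU and HVNI.
- P(both) = p1·p2 + phi·√[p1(1−p1)p2(1−p2)]; P(TAU only) = p1 − P(both); P(HVNI only) = p2 − P(both); P(neither) is the remainder.
- Exact McNemar, with b TAU-only and c HVNI-only subjects: p = 2·Σ C(b+c, k)·0.5^(b+c) for k = 0 to min(b, c), capped at 1. For b ≠ c, mid-p subtracts the probability of the observed split once.
- Fisher uses only the totals, both + b and both + c, each out of 26.
- Power and type I error: sum the multinomial probabilities of all possible tables of 26 subjects in which p < 0.05.

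**Same totals, different pairing.** Suppose 15 of 26 have the event on TAU and 8 of 26 on HVNI.

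| Event in both | TAU only / HVNI only | Fisher p | Exact McNemar p |
|---|---|---|---|
| 0 | 15 / 8 | 0.093 | 0.210 |
| 5 | 10 / 3 | 0.093 | 0.092 |
| 6 | 9 / 2 | 0.093 | 0.065 |
| 7 | 8 / 1 | 0.093 | 0.039 |
| 8 | 7 / 0 | 0.093 | 0.016 |

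For example, with 8 and 1 discordant: 2·(1 + 9)/2⁹ = 20/512 = 0.039. Fisher's p-value never moves. Eight in both is the largest overlap these totals allow.

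**Power at n = 26.**

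| TAU vs HVNI | phi | Fisher | Exact McNemar | Mid-p |
|---|---|---|---|---|
| 60% vs 30% | 0.5 | 47% | 80% | 89% |
| 60% vs 30% | 0.3 | 48% | 62% | 72% |
| 60% vs 30% | 0 | 48% | 47% | 56% |
| 60% vs 30% | −0.3 | 48% | 39% | 47% |
| 30% vs 10% | 0.3 | 29% | 36% | 51% |
| 20% vs 5% | 0.3 | 17% | 19% | 33% |
| 15% vs 5% | 0.3 | 5% | 6% | 13% |

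The first row lies near the limit of what is possible. At 60% vs 30%, phi cannot exceed (0.30 − 0.18)/√(0.24 × 0.21) = 0.12/0.2245 = 0.53. At phi = 0.5 only 0.8% of subjects have the event on HVNI alone. The rows at 0.3 and 0 are the more cautious guide.

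**Type I error at 50% vs 50%, nominal 5%.**

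| phi | Fisher | Exact McNemar | Mid-p |
|---|---|---|---|
| 0.5 | 0.2% | 1.5% | 3.4% |
| 0 | 2.5% | 2.5% | 4.4% |
| −0.3 | 4.6% | 3.0% | 4.8% |

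**The case against.** The strongest reply is that no planned analysis is shown to be affected. No listed endpoint is categorical, the data list in Section VII holds no yes/no variable, and adverse events and exacerbations are to be recorded without any statement that they will be tested between sessions. This stands as a limit on reach.

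A second reply is that the Fisher sentence may refer back to the baseline characteristics mentioned earlier in Section VIII, where associations across different subjects (GOLD stage or long-term oxygen use, say) would suit it. That reading is possible, but the protocol names no such analysis and defines no subgroups. With a single cohort, baseline offers no two treatment groups to compare. The sentence then has no stated use for which it is valid, and it still needs correcting.

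A third reply concerns size. The largest gains need a correlation near its upper limit. For rare events, which adverse events may well be, exact McNemar adds one or two points of power at most in the cases above. At zero correlation Fisher is marginally ahead of it. Much of the mid-p gain at low rates comes from a less conservative test, not from pairing. All of this is correct. It bounds the consequence but does not make an independent-groups test suitable for paired data.

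**Conclusion.** The concern holds. The stated rule does not fit the design, and the plan supplies neither a paired categorical test nor independent groups for Fisher's test to compare. In the 60% vs 30% case the loss against exact McNemar is about 14 percentage points of power at correlation 0.3 (62 − 48) and 33 at 0.5 (80 − 47). There is no loss at zero correlation, and at −0.3 Fisher rejects more often, under the null as well. These sizes rest on assumed rates and correlations, 26 subjects with both sessions, and a two-sided 0.05 level. The listed endpoints and the sample size are not touched. The correction should be made, but the validity of the main comparison does not depend on it.

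**What to change.** Replace the Fisher sentence in Section VIII with wording such as:

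> Binary variables compared between sessions are analysed with McNemar's test (exact or mid-p, fixed before data are seen) and reported with the paired difference in proportions and its 95% confidence interval. Paired variables with more than two categories use an exact test of marginal homogeneity.

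Name the categorical variables to be compared, and say whether 18-minute completion and desaturation are among them. Summarise baseline characteristics of the single cohort descriptively, without a between-session test. Keep Fisher's test only for independent subgroups, if any are intended and named.

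The cost is a change of wording. Both sessions are already recorded for each subject, so no new data or subjects are needed. The paired test does not remove the confounding of treatment with the fixed TAU-then-HVNI order, and the report should say so.
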